10.2 Tipping Point Analysis

The tipping point analysis will create a type of figure called a heat map. It will not impute data at the subject level, but rather will be based on the observed total counts of TEAR status and number of missing values per group.

The steps are summarised below:

For purposes of the code below, set

```
Nm = Total # of subjects randomized to MYL-1601D group
Nn = Total # of subjects randomized to Novolog group
Mm = # of subjects missing TEAR status in MYL-1601D
group
Mn = # of subjects missing TEAR status in Novolog group
TEARm = # of subjects in MYL-1601D group who are TEAR
positive
TEARn = # of subjects in Novolog group who are TEAR
positive
```

Then run code similar to the following. The code below assumes that the above variables have been created as global variables.

```
%macro heat;

data heatmap;
do i = 0 to &mn;
  do j = 0 to &mm;
    y = &tearn + i;
    x = &tearm + j;
    pn = y/&nn;
    pm = x/&nm;
    riskdiff = pm - pn;
    margin = (quantile('NORMAL',0.95) +
    quantile('NORMAL',0.90))*
    sqrt(2*pn*(1-pn)/&nn);
    output;
  end;
end;
run;

%do i = 0 %to &mn;
  %do j = 0 %to &mm;

    data imputed;
    length group $8;
    group="NOVOLOG";
    status=1;
    count=%eval(&tearn+&i);
    output;
    status=0;
    count=%eval(&nn - (&tearn+&i));
    output;
```

```

group="MYL-1601D";
status=1;
count=%eval(&tearm+&j);
output;
status=0;
count=%eval(&nm - (&tearm+&j));
output;
run;

ods exclude all;
proc freq data=imputed;
table group * status / riskdiff (cl=WALD column=2)
alpha=0.1;
weight count;
ods output riskdiffcol2=rdiff1;
run;
ods exclude none;
data ci;
set rdiff1 (where=(row="Difference"));
y = &tearn + &i;
x = &tearm + &j;
run;

data heatmap;
merge heatmap
ci (keep=x y risk ase lowercl uppercl)
;
by x y;
length color $8 digits $16 a1-a6 asterisk $1;
if -0.0000001 <riskdiff < 0.0000001 then do;
red=255;
green=255;
blue=255;
end;
else if riskdiff > 0 then do;
if riskdiff >= 0.16 then do;
red = round(484 - (1435*riskdiff));
green = 0;
blue = 0;
end;
else do;
red = 254;
green = round(255/(1+exp(-32.96*(0.1149-
abs(riskdiff)))));
blue = round(255/(1+exp(-21.58*(0.0793-
abs(riskdiff)))));

```

```

        end;
    else if . < riskdiff < 0 then do;
        red = round(255/ (1+exp(-18.51*(0.1108-
abs(riskdiff)))));
        green = round(255/ (1+exp(-27.85*(0.1699-
abs(riskdiff)))));
        blue = round(255/ (1+exp(-20.10*(0.1024-
abs(riskdiff)))));
    end;

    digits = "0123456789ABCDEF";
    n1 = floor(red/16);
    n2 = red - (n1*16);
    a1 = substr(digits,n1+1,1);
    a2 = substr(digits,n2+1,1);
    n3 = floor(green/16);
    n4 = green - (n3*16);
    a3 = substr(digits,n3+1,1);
    a4 = substr(digits,n4+1,1);
    n5 = floor(blue/16);
    n6 = blue - (n5*16);
    a5 = substr(digits,n5+1,1);
    a6 = substr(digits,n6+1,1);
    color = compress("CX"||a1||a2||a3||a4||a5||a6);

    if (lowercl < (margin) < uppercl) and
        (lowercl < (-margin) < uppercl) then asterisk=" ";
    else asterisk="*";

    run;

    %end;
%end;
%mend heat;

%heat;
```

This code will create a dataset called HEATMAP that contains the X and Y variables, risk difference, and color to use for the plot. There will be (Mm+1) values on the x-axis and (Mn+1) values on the y-axis. These will be the number of subjects with TEAR=1 in the MYL-1601D (x-axis) and Novolog (y-axis) groups, respectively, based on all possible counts that could be observed if the missing TEAR values were known. The HEATMAP dataset provides these counts as variables x and y for each row.

The heat map figure will consist of a grid with dimensions (Mm+1) × (Mn+1). The x-axis

will be labeled with the range of values of the variable x in the HEATMAP dataset, and the y-axis will be labeled with the range of y values. Each row in the HEATMAP dataset corresponds to one rectangle on the grid. Within that one rectangle should be printed the value of the variable RISKDIFF. If the value of RISKDIFF lies outside the margin, then an asterisk should be appended to the numeric value of RISKDIFF. A variable ASTERISK has been created in the sample code for this purpose.

The rectangle itself should be filled with color, which will be generated based on the value of RISKDIFF. Shades of red color will indicate that the TEAR rate is higher in the MYL-1601D group, while green shades will indicate a higher TEAR rate in the Novolog group. The color intensity will increase as the magnitude of RISKDIFF becomes more extreme. Colors will be programmatically assigned and will be captured in hexadecimal format in the variable COLOR in the HEATMAP dataset. This hexadecimal value can be supplied to the SAS graphics procedure.

The heat map will display the number of TEAR events in the MYL-1601D group in descending order on the x-axis and number of TEAR events in the Novolog group in descending order on the y-axis. An example is provided in the figure shells.

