02 MAR 2020
Date
(DD MMM YYYY)

[name]
[name], Senior Program Manager

02 Mar 2020
Date
(DD MMM YYYY)

Approved at Mylan Pharmaceutical Inc by:

[name], Principal Biostatistician

02 Mar 2020

Date
(DD MMM YYYY)

REVISION HISTORY

Version/Date	Version name	Section	Changes implemented
FINAL 1.0/11JAN2019	Final Version 1.0	Not Applicable	Not Applicable
FINAL 2.0/18OCT2019	Final Version 2.0	7.2.1 8.1 8.7.1 8.7.2 8.7.3.1 8.7.5 8.8.4 8.8.5 8.9 10.1 10.2 10.3	Updated missing data analysis method for primary analysis due to immunogenicity assay method changes Updated imputation for retests, unscheduled visits and visit end of treatment; updated visit window Updated analysis methods for primary endpoint Updated primary efficacy analysis method and tipping point analysis due to immunogenicity assay method changes Added sensitivity analysis for HbA1c Updated subgroup analysis method Updated the definition for relative hypoglycemia Updated Immunogenicity assessments Updated the incidence analyses for lab data, vital signs, physical examination and ECG Updated multiple imputation method SAS code, added multiple imputation for HbA1c Updated example SAS code for tipping point analysis method Updated SI units for laboratory category table
FINAL V3.0/ 02MAR2020		6.1 6.2 6.3	Add randomized analysis set definition. Modified ITT analysis set to exclude subjects who are in the site with GCP violation Modified PP analysis set to exclude subjects who are in the site with GCP violation and also add more clarification for PP analysis set.

		6.4	Modified Safety analysis set to exclude subjects who are in the site with GCP violation
		7.2	Change single imputation into multiple imputations for missing baseline value.
		7.3	Add a section address GCP issue at one investigator site (Site ID: 6103) and add sensitivity analysis without inclusion of data from this site
		10.0	Add SAS programming flow chart per regulatory request

TABLE OF CONTENTS

SIGNATURE PAGE2

REVISION HISTORY4

TABLE OF CONTENTS6

LIST OF ABBREVIATIONS8

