6 ANALYSIS POPULATIONS

6.1 Randomized analysis set

Randomized analysis set include all subjects who are randomized into the study.

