6.2 ITT analysis set

The ITT analysis set includes all randomized subjects without being in the site with GCP violation (including subjects who receive incorrect treatment, do not complete the study or do not comply with the protocol or used prohibited medication, randomized but do not take any study drug). The subjects who are in the site with GCP violation will be excluded from ITT analysis set.

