7.3 Handling of site with GCP violation

During routine monitoring of this study, it was observed that one site (Site ID: 6103) had GCP compliance issues, which raised doubts on the study conduct. The blinded ADA results from the site also confirmed the need to exclude the site from results reporting. Mylan decided to conduct statistical analyses to exclude this site from ITT, Safety, and PP analysis sets. Additional sensitivity analysis to include this site (Randomized analysis set) for major baseline findings, efficacy and safety analysis will be performed. The purpose of the sensitivity analysis is to determine if major efficacy and safety analyses remain consistent with inclusion data from this site.

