8.7 Efficacy analyses

This section addresses separately the analyses to be conducted on the primary and secondary efficacy variables. The primary analysis population for efficacy analyses will be the ITT population, although some analyses may be repeated for other analysis sets as indicated.

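### The tipping-point denominators in SAP 10.2 are still worded as all randomized subjects and no longer match the ITT set of the primary analysis, which since SAP v3 leaves out site 6103

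*SAP*

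**What the plan says.** SAP 10.2 builds the heat map from six counts. The two denominators are "Nm = Total # of subjects randomized to MYL-1601D group" and "Nn = Total # of subjects randomized to Novolog group". The missing counts, for example "Mn = # of subjects missing TEAR status in Novolog group", and the two TEAR-positive counts name no analysis set.

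The analysis sets are in SAP section 6. For the Randomized set (6.1): "Randomized analysis set include all subjects who are randomized into the study". For ITT (6.2): "The subjects who are in the site with GCP violation will be excluded from ITT analysis set". The revision history enters the second as a version 3.0 change: "Modified ITT analysis set to exclude subjects who are in the site with GCP violation". For section 10 the same version lists only an added programming flow chart, with no change to the 10.2 definitions.

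SAP 8.7 states: "The primary analysis population for efficacy analyses will be the ITT population". SAP 8.7.1 repeats this for the primary endpoint, and 8.7.2.2 lists the tipping point among the sensitivity analyses of that endpoint. The Randomized set has a separate use in 7.3: "Additional sensitivity analysis to include this site (Randomized analysis set".

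**The concern.** A tipping-point analysis asks how far the missing outcomes would have to lean before the primary conclusion changes. It answers that only if the observed part of every cell is the primary analysis's own data. In 10.2 the denominators enter both rates, the risk difference, the margin, the count of TEAR-negative subjects (N minus positives) and so the Wald limits of every cell.

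Taken as written, there are two ways to fill in the other four counts:

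- **From ITT.** Site 6103 subjects are then in the denominators but in neither the positive nor the missing counts. They fall into the TEAR-negative remainder.
- **From all randomized subjects.** The map then describes the Randomized set. It includes ADA results that 7.3 gives as a reason for leaving the site out.

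Either map could be read as showing how robust the ITT result is when it was not computed on the ITT subjects.

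**Working it through.** **1. Reproduce the plan's margin.** Per cell, 10.2 uses margin = (z0.95 + z0.90) × √(2·pN(1−pN)/nN), with multiplier 1.645 + 1.282 ≈ 2.926. With nN = 250 this gives 5.70 points at 5%, 10.47 at 20%, 11.99 at 30% and 13.09 at 50%. SAP Table 2 has 5.7, 10.5, 12.0 and 13.1. All 12 rows agree to within 0.05 points.

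**2. Assumptions for sizing.** The documents give about 500 subjects and about 200 sites, so 500/200 = 2.5 subjects per site on average. Site 6103's size and results are not given. Assume 250 randomized per arm, 10 per arm at the site (ITT n = 240 per arm) and 24 ITT subjects per arm with missing status, so 25 × 25 = 625 cells. Observed ITT positives are 11 per arm (11/216 ≈ 5%) or 43 per arm (43/216 ≈ 20%). A cell meets equivalence if the 90% Wald interval, difference ± 1.645·SE, lies within ± margin.

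**3. Margin in the zero-imputed cell, 5% case.**

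- All counts from ITT: pN = 11/240 = 0.0458; 2.926 × √(2 × 0.0458 × 0.9542/240) = 5.6 points.
- Site added, every site subject positive: pN = 21/250 = 0.084; 2.926 × √(2 × 0.084 × 0.916/250) = 7.3 points.

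**4. Cells meeting equivalence, of 625.**

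| Case | All counts ITT | ITT counts, randomized N | All randomized, site all positive |
|---|---|---|---|
| 5%: cells | 347 | 348 | 392 |
| 5%: margin, zero-imputed cell | 5.6 | 5.4 | 7.3 |
| 20%: cells | 451 | 454 | 470 |
| 20%: margin, zero-imputed cell | 10.2 | 9.9 | 10.7 |

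With wrong denominators only, 1 cell changes verdict at 5% and 3 at 20%. One cell at 5% lies on the boundary: with the unrounded normal quantile in the limits, the ITT count is 348 and no cell changes.

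**5. A site nearer the average.** With one site subject per arm on the same 625-cell grid, the denominator error alone changes 0 cells (5%) and 1 cell (20%). If both site subjects are positive, 5 and 3 cells change, and the margins move from 5.39 to 5.60 and from 9.91 to 9.97 points.

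**6. Unbalanced sites.** Assume 12 missing per arm (169 cells) and ITT rates of 10%, 30% and 50%. Across both readings, with all site subjects positive in the second:

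| Site subjects (MYL-1601D + NovoLog) | Largest shift in risk difference | Cells changing verdict |
|---|---|---|
| 2 + 1 | 0.4 points | 0 to 4 |
| 10 + 6 | 1.6 points | 0 to 17 |
| 13 + 7 | 2.3 points | 0 to 31 |

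**7. Merge order.** HEATMAP is written with y (NovoLog) in the outer loop and x (MYL-1601D) in the inner loop, then merged by x and y without a sort. With 75 observed positives and one missing subject per arm, the (x, y) order is (75,75), (76,75), (75,76), (76,76). The third row breaks x-then-y order. The order fails whenever both arms have at least one missing subject, and the merge step then stops with a sort error.

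**8. Asterisk rule.** The code leaves the star off only if the interval contains both +margin and −margin. At equal rates the interval reaches 1.645·SE either side of the difference and the margin is 2.926·SE, so the interval is too short to contain both. On a 16 × 16 grid with 250 per arm and rates of 10%, 30% and 50%, all 256 cells are starred, although 216, 249 and 254 of them meet equivalence.

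**The case against.** The strongest reply is that the body of the SAP already settles the population. Section 8.7 makes ITT the default for efficacy analyses, 8.7.2.2 attaches the tipping point to the primary analysis, and 7.3 treats the Randomized set as an extra. The 10.2 wording does not use the formal name of the Randomized set and could mean only arm as assigned. A programmer who applied the ITT default would take all six counts from ITT and get the right map. This stands in part: one cannot say that the map will include site 6103. But it asks the programmer to set aside a written definition, so the passages still need reconciling.

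It can also be said that Protocol 7.4 defines ITT as all randomized subjects, so a map on that set is not meaningless. That probably explains the wording, and it supports a second map. It does not supply one for the SAP's primary analysis.

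On size, the larger shifts need a site well above average with every subject TEAR positive. That is correct. SAP 7.3 hints that the site's ADA results were unusual, but does not say how.

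On the code, 10.2 offers it as an example, and a sort error is visible and easily repaired. That also stands, and it is why the merge is a minor point. The asterisk rule is different, because it would run cleanly and mislead.

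**Conclusion.** The point holds as a conflict between an appendix definition and the primary analysis set. Followed literally, 10.2 does not test the ITT primary result. Its effect cannot be sized from the documents. On the assumptions above, the denominator error alone changes at most 3 of 625 cells, and an average-size site changes few. The shift from 5.6 to 7.3 points, and from 347 to 392 cells, rests on 10 site subjects per arm, all positive, at about a 5% rate. In that case the error widens the margin and adds passing cells, so it flatters robustness.

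A reader might infer more than the documents support:

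- **That the primary equivalence result is affected.** It is not; 10.2 feeds only the heat map.
- **That this is the plan's main check on missing data.** SAP 8.7.2.2 lists three sensitivity analyses without ranking them.
- **That the unsorted merge gives a wrong answer or ends the whole run.** It stops the merge step, and only when both arms have missing status. Whether the session halts depends on how SAS is run.
- **That sorting repairs the map.** It does not, because the asterisk rule would still star every cell in the grids checked.

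**What to change.** In SAP 10.2, define Nm, Nn, Mm, Mn, TEARm and TEARn on the ITT set used for the primary analysis, by assigned arm. If a map including site 6103 is wanted under 7.3, produce it as a second, labelled figure with all six counts from the Randomized set.

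In the code, sort HEATMAP by x and y before the merge, or make x the outer loop. Rewrite the asterisk condition so that a cell is starred when the 90% interval is not wholly within ± margin, i.e. unstarred only if the lower limit exceeds −margin and the upper limit is below +margin. Align the 10.2 text, which ties the star to the risk difference lying outside the margin, with that rule.

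The cost is six definitions, one sort step, one condition and one sentence of text. No new data are needed and the primary analysis does not change.

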10.3 Laboratory Category

Laboratory Category	Parameter (SI unit)	Potentially Clinically Significant Low	Potentially Clinically Significant High
Hematology	WBC (10^9 L^{-1})	<2.0	>20.0
	Neutrophil count (10^9 L^{-1})	<1.0	NA
	Hemoglobin (g/L)	<80	>200
	Platelets (10^9 L^{-1})	<50	>999
Biochemistry	ALT (U/L)	NA	>3XULN
	AST (U/L)	NA	>3XULN
	ALK phosphatase (IU/L)	NA	>3XULN
	Total Bilirubin (umol/L)	NA	>2XULN
	Glucose (mmol/L)	<3.1	>15.0
	Creatinine (umol/L)	NA	>1.5XULN
	BUN (mmol/L)	NA	>21.4
	Sodium (mmol/L)	<130	>155
	Potassium (mmol/L)	<3.0	>6.0
	Total Protein (g/L)	NA	>95
	Albumin (g/L)	<20	NA

Laboratory Category	Parameter (SI unit)	Potentially Clinically Significant Low	Potentially Clinically Significant High
	Calcium (mmol/L)	<1.8	>3.1
Lipids	Triglycerides (mmol/L)	<0.1	>10.2
	Total Cholesterol (mmol/L)	<0.5	>10.3
	LDL Cholesterol (mmol/L)	<0.5	>9.0
	HDL Cholesterol (mmol/L)	<0.5	NA

Variable	Unit	Low	High
SBP	mm Hg	≤ 90 mmHg AND change from baseline ≤ -20 mmHg	≥ 180 mmHg AND change from baseline ≥ 20 mmHg
DBP	mm Hg	≤ 50 mmHg AND change from ≤ -15 mmHg	≥ 105 mmHg AND change from baseline ≥ 15 mmHg
Heart rate	Bpm	≤ 50 bpm AND change from baseline ≤ -15 bpm	≥ 120 bpm AND change from baseline ≥ 15 bpm
Body temperature	°C	NA	≥ 38.3 °C AND change from baseline ≥ 1.1 °C
Weight	Kg	percentage change from baseline ≤ -7.0 %	percentage change from baseline ≥ 7.0 %
